15.10 Rescue Treatment

Patients with no spontaneous bowel movement for 3 consecutive days will be authorized to use rescue, if they wish to. The patients will not be required to contact the investigator prior to taking any medication/supplement but they will be required to declare the rescue medication on their eDiary. The following treatment is recommended (not by order):

- 1. Dulcolax® suppository/bisacodyl suppository
- 2. Fleet Enema®
- 3. Dulcolax®/bisacodyl tablet (1x5mg)

If the patient takes a rescue medication/supplement that is not in the above list, the patient will need to give a reason for it in his eDiary.

If the investigator prescribes a rescue medication/supplement that is not in the above list, the investigator will need to mention it and give the reason in a note to file or appropriate form.

Doc No: 220CLD

Rev: 03 Date: August 26, 2016

Page 47 of 93

Patients who take rescue medication three times or more during the run-in period will be considered as screening failures.

A spontaneous bowel movement is defined as a bowel movement that occurs at least 24h after laxative/rescue intake and without digital maneuver.

A complete spontaneous bowel movement is defined as a spontaneous bowel movement associated with a feeling of complete evacuation by the patient.

15.11 Termination visit

After 6 weeks, treatment will be ceased. Patients will visit again the medical center for evaluation and completion of the Rome III questionnaire, Bristol Stool Scale and study end form. The patient will be evaluated for occurrence of adverse events, concomitant medication/rescue and compliance to the eDiary.

The patients will bring back all remaining capsules in their possession as well as the base unit.

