12. STUDY OBJECTIVE

The objectives are to assess the ease of use, tolerability, safety and efficacy of a new frequency of Vibrant Capsule administration: one per day for 2 days, followed by one day without (14 capsules in 3 weeks).

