In addition, patients will undergo a physical examination including digital rectal examination, vital sign measurements and blood tests.

Patients will then fill in the Rome III questionnaire to confirm the diagnosis of Chronic Idiopathic Constipation and fill out the Bristol Stool Scale. Findings will be recorded on the eCRF.

Eligible patients will then be asked to refrain from taking any medication or supplement they are using to relieve their constipation, and will perform a self-assessment of their normal spontaneous bowel movements for 14 days (run-in period), on the eDiary. Patients will also be asked to record clinical symptoms and usage of any medication or supplement on the eDiary during the run-in period.

After 14 days the patients will visit the medical center for the baseline visit. Eligibility will be re-assessed and confirmed based on the patient's completed eDiary and Rome III questionnaire. The patient will be trained in the medical center to use the base unit. He will activate himself the first capsule and will ingest it in front of the medical staff. All the other capsules will be ingested from the home of the patient. Only the first ingestion will take place in the medical center.

During the treatment period, patients will ingest Vibrant Capsule using the following sequence: one per day for 2 days, 1 day without, one per day for 2 days, 1 day without, etc. The patient will ingest a total of 28 capsules in 6 weeks considering the sequence.

Capsule intake will always be performed at the same time: during the evening, between 9 PM and 10 PM.

Doc No: 220CLD

Rev: 03 Date: August 26, 2016

Page 43 of 93

After 6 weeks, treatment will be ceased and patients will visit the medical center one last time for evaluation and completion of Rome III questionnaire, Bristol Stool Scale and other assessments.

Patients will be instructed to complete a simple patient eDiary throughout the duration of the study. This will include daily recordings of number and time of bowel movements, clinical symptoms and medication/supplements usage, including rescue medication.

Please refer to section 15.15 for a detailed study schedule.

Data collection will include physician identification, investigational device identification data and usage of the capsule. This data will be documented on the eCRF, together with the occurrence of any adverse events during the capsule usage.

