15.9 Treatment

On day 0 (baseline visit), the patient will arrive to the clinic. Eligibility will be reassessed and confirmed based on the Rome III questionnaire and on the patient's completed diary. Based on the Vibrant Capsule's intended use, patients need to have an average of at least 1 SBM per week but less than 3 SBM per week during the two weeks of run-in.

The Bristol Stool Scale will be completed.

Eligible patients will take the Vibrant Capsules. The study is open-label.

Treatment duration is 6 weeks.

The patient will be trained by the study coordinator to activate the Vibrant Capsules using the base unit. After an oral explanation, the patient will read the label, and the study coordinator will make sure the patient fully understands how to use the base unit. The patient will then activate his/her first capsule, in front of the study coordinator, and swallow it.

The patient will be released home with the base unit and capsules for the first three weeks of treatment. He/She will be asked to continue with the daily completion of the eDiary. Actual point of enrollment for the patient is considered the day of first capsule intake.

Patients will be asked to refrain from any medication or supplement they are using to relieve their constipation, throughout the treatment period. A rescue treatment will be authorized upon need (refer to section 15.10 for details).

Capsule intake will be performed during the evening between 9 PM and 10 PM. Only the first intake, which is in the medical center, will not take place at such a time.

Doc No: 220CLD

Rev: 03 Date: August 26, 2016

Page 46 of 93

Half of the capsules the patient is scheduled to take will be provided at the baseline visit. The patient will be provided with the second half of the capsules during a mid-treatment visit to the medical center (day 21).

The first week of treatment, the patient will receive two short phone calls from the study coordinator. Starting the second week of treatment, he will receive one phone call per week.

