16.7 Follow- Up of Unresolved Events

All adverse events should be followed until they are resolved or the subject's participation in the study ends.

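### Planned adverse-event observation ends about 1.5 to 1.8 days after the last scheduled capsule, and the visit-4 window is not reconciled with the capsule sequence

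*Combined protocol and SAP*

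**What the plan says.** Section 15.1 gives the sequence as "one per day for 2 days, 1 day without, one per day for 2 days, 1 day without, etc" and the total as "The patient will ingest a total of 28 capsules in 6 weeks considering the sequence". Section 12 gives the matching rate of 14 capsules per 3 weeks. Section 15.9 starts treatment in clinic ("On day 0 (baseline visit), the patient will arrive to the clinic"), where the first capsule is swallowed. For the others, "Capsule intake will be performed during the evening between 9 PM and 10 PM".

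Section 15.11 states "After 6 weeks, treatment will be ceased" and then describes the termination visit, at which all remaining capsules and the base unit are handed back. Section 15.1 uses the same order and says "patients will visit the medical center one last time for evaluation". Table 11 (Section 15.15) puts this visit on day 42, ±1-2 days, and has no later column. Section 14.3 totals 8 weeks, made up of run-in and treatment only.

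On adverse events, Section 16.7 says "All adverse events should be followed until they are resolved", or until participation ends if that comes first. Section 28 promises follow-up to resolution only for subjects removed because of an adverse event. Section 15.14 allows a follow-up clinic visit when necessary, but schedules none.

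**The concern.** Safety and tolerability are stated objectives (Section 12), and the safety endpoint is all adverse events (Section 17.2.3). The device has to travel through the gut of patients selected for 1 to fewer than 3 spontaneous bowel movements (SBMs) per week. If the last planned contact comes very soon after the last capsule, a new event that begins later, including one connected with passage of that capsule, has no planned route into the database.

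There is also a mismatch in the calendar. Sections 15.1 and 15.11 have the visit follow the end of treatment, but the Table 11 window is not tied to the last intake and, on its widest reading, opens before it.

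**Working it through.** **Inputs.**
- Two days on and one day off, 28 capsules in 6 weeks (Section 15.1)
- First capsule on day 0, later ones at 21:00-22:00 (Section 15.9)
- Visit 4 on day 42 ±1-2 days (Table 11)
- Run-in rate of at least 1 and below 3 SBMs per week (Section 15.9)
- Assumption: visits take place between 09:00 and 17:00, as the documents give no hour

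**Step 1: reproduce the plan's count.** Intake days are d = 0 to 41, leaving out every third day (2, 5, 8, ...). That gives 42 × 2/3 = 28 capsules, with 21 × 2/3 = 14 in days 0-20. Both match the protocol. The last four intake days are 36, 37, 39 and 40, so the last scheduled capsule is on day 40 at 21:00-22:00.

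**Step 2: time from the last scheduled capsule to visit 4.** Interval in hours = 24 × (visit day − 40) + clinic hour − intake hour. The shortest case pairs 09:00 with 22:00, and the longest pairs 17:00 with 21:00.

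| Visit 4 on day | Hours | Days |
|---|---|---|
| 40 | −13 to −4 | −0.54 to −0.17 |
| 41 | 11 to 20 | 0.46 to 0.83 |
| 42 (nominal) | 35 to 44 | 1.46 to 1.83 |
| 43 | 59 to 68 | 2.46 to 2.83 |
| 44 | 83 to 92 | 3.46 to 3.83 |

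**Step 3: what a day-40 visit means.** The negative interval says that the visit precedes that evening's scheduled capsule. Capsules and base unit are returned at the visit, so the patient has neither a capsule nor the means to activate one that evening. The last capsule taken is then that of day 39, with 24 + 9 − 22 = 11 h to 24 + 17 − 21 = 20 h of observation, or 0.46 to 0.83 days.

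**Step 4: how much exposure is affected.** At a day-42 visit the day-37 capsule has had 120 + 9 − 22 = 107 h to 120 + 17 − 21 = 116 h, or about 4.5 to 4.8 days. Every earlier capsule has had longer. Only the capsules of days 39 and 40 have less than that: 2/28 = 7% of the capsules.

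**Step 5: a rough yardstick.** At 1 to 3 SBMs per week the mean interval between SBMs is 7/1 = 7 days to 7/3 = 2.3 days. The nominal 1.5 to 1.8 days is shorter than either.

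**Sensitivity to the baseline window.** Table 11 lets the baseline visit fall up to 2 days after day 0. If visit 4 is still counted from the nominal day 0, a first capsule taken 1 day late moves the last to day 41 and leaves 0.46 to 0.83 days before a day-42 visit. Two days late moves it to the evening of day 42, after the visit. If days are counted from the first capsule, nothing changes. The documents do not say which count applies.

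**The case against.** Three stronger readings are tempting, and the documents support none of them.

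- A reader might infer that a capsule could be swallowed after the final visit with no observation at all. The return of capsules and base unit in Section 15.11 rules this out. The result of a day-40 visit is a lost capsule and short observation of the one before it.
- A reader might infer that most subjects still carry the last capsule at visit 4. With a constant SBM rate and no treatment effect, the chance of no SBM is exp(−1 × 1.5/7) = 0.81 at one per week over 1.5 days and exp(−3 × 1.8/7) = 0.46 at three per week over 1.8 days. These are chances of no SBM, not of retention. Under Section 15.10, movements within 24 h of rescue or with digital maneuver are not SBMs, yet they could expel a capsule. Conversely, the first SBM need not carry the last capsule.
- A reader might infer that reported incidence is materially too low. Section 17.8.7 tabulates the percentage of subjects with events. A subject is missed only if the event first appears after roughly the last two capsules and beyond the final contact. Earlier exposure is covered by the coordinator calls, the mid-treatment visit and the assessment at each evaluation. The shortfall may be small.

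It is also fair to say that the tolerance in Table 11 is ambiguous. Read as ±1 day, the earliest visit follows the day-40 capsule by about half a day. The mode of operation, much of the risk section, the earlier human investigations and the diary are not visible in the public text, so time of action and transit cannot be checked, and their absence is no fault of the plan. This is a descriptive pilot study.

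These points limit the claim but do not remove it. The discretionary visit in Section 15.14 is not a planned contact, and Section 28 does not capture new events after an ordinary final visit.

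**Conclusion.** The point holds in a limited form. If the trial runs exactly as written, planned adverse-event observation after the last scheduled capsule is about 1.5 to 1.8 days at the nominal visit, 0.5 to 0.8 days at day 41 and at most about 3.8 days at day 44. At a day-40 visit one capsule is lost and about half a day or slightly more of observation follows the day-39 capsule.

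The figures rest on counting days from the first capsule and on the assumed clinic hours. The day-40 case also needs the minus-2 reading of the window. The number of events missed cannot be computed from the documents, and the SBM interval is only a rough guide to passage. The gap touches a stated safety objective and costs little to close. It does not call the bulk of the safety data into question.

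**What to change.** Add one scheduled coordinator call, asking about adverse events and capsule passage, at a stated interval after the last capsule and later than visit 4. Without a stated interval the call could fall on day 41 and add nothing. One option is about 7 days, the longest mean SBM interval among eligible subjects. From a day-40 capsule that gives day 40 + 7 = 47, which is after the latest visit-4 date of day 44. The sponsor may prefer another interval justified from its own transit data. Enter the call in Table 11, and name it in Section 16.7 as the end of adverse-event collection.

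Separately, reconcile the visit-4 window in Table 11 with Sections 15.1 and 15.11 so that the visit does not precede the last scheduled capsule. State whether the tolerance is 1 or 2 days and from which day visits are counted.

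The cost is one call of 5-10 minutes per subject, made by coordinators who already call weekly about adverse events, and about one more week of participation. The duration statements in the Synopsis and Section 14.3 need a matching edit. No change to eligibility or sample size follows.

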15.12 Concomitant medication

All medication taken by the patient in addition to the investigational device is termed concomitant medication. All concomitant medication taken during the study must be documented in the case report form (name of drug, date of intake, dosage, number of takes per day, reason for medication). The patient will fill in all the information daily on the eDiary.

15.13 Prohibited medication

The medications listed below will be prohibited during the entire study:

- Medications that may affect intestinal motility
- Prokinetics
- Antidepressants
- Anti-Parkinsonian medications
- Opiates
- Opioids
- Calcium-channel blockers
- Aluminum/magnesium hydroxide.

Chronic use of non-steroidal anti-inflammatory drugs (NSAIDs) is also prohibited. Chronic use is defined as taking full dose NSAIDs on a regular basis (i.e. more than three times a week) for at least six months.

Patients on cardiac doses of aspirin may be enrolled in the study.

The following medications are equally prohibited, but with an exception when the subject has been on a stable dose of the medication for at least 3 months:

- Antidepressants
- Thyroid or hormonal replacement therapy.

Doc No: 220CLD

Rev: 03 Date: August 26, 2016

Page 48 of 93

15.14 Recording

All tests will be performed prior to procedure in case where not already done per routine hospital protocol. Device handling and function will be recorded.

The standard treatment and care provided to all patients, alongside the Vibrant capsule and other treatments will be performed and recorded on the appropriate study eCRF. The patient will be questioned on his clinical status, the presence of any medical intervention performed since the last visit and any adverse events or discomforts. When necessary, the patient will be asked to arrive for a follow-up visit at the clinic.

15.15 Study Schedule

Table 11 summarizes the required data collection from assessments and tests performed during the study.

Procedures	Screening	Baseline	Mid-treatment visit	Termination visit
Visit No.	1	2	3	4
Day	-14	0 (+1-2 days)	21 (±1-2 days)	42 (±1-2 days)
IC	+			
Eligibility Criteria	+	+		
Physical Exam	+			
Digital Rectal Exam	+			
Vital Signs	+			
Lab Data	+	+		
Administration of capsule		+		
Rome III	+	+		+
Bristol Stool	+	+	+	+
Patient eDiary	+	+	+	+
Adverse Events	+	+	+	+
Concomitant Medication	+	+	+	+

Table 11 – Study Schedule of Assessments

Doc No: 220CLD

Rev: 03 Date: August 26, 2016

Page 49 of 93

15.16 Deviations from study protocol

Any deviation from the study protocol should be notified to the sponsor, documented on study deviation forms and reported to the Ethics Committee as required.

15.17 Investigative Center Selection Criteria

The investigative site will meet the following selection criteria prior to inclusion in this study:

- Clinical research study experience and resources that demonstrate good compliance with study requirements and timely, complete documentation of subject follow-up.
- Sufficient subject volume to meet enrollment timeframe.

16. ADVERSE EVENTS RECORDING

At each evaluation, the investigator will determine whether any adverse events (AE's) have occurred. All adverse events occurring during the study will be recorded on the appropriate case report form page by the investigator. The nature, severity and relation of the adverse event to the study device will be documented.

16.1 Reporting Requirements

Timely and complete reporting of Adverse Events (AE) and safety assessment allows:

- Protection of safety and study subjects.
- Greater understanding of the overall safety profile of the study treatment.
- Appropriate modification of study protocols and improvement in study design and procedures.
- Adherence to regulatory requirements.

The definitions and reporting requirements adopted in this study are derived from the current International standard on clinical investigations: Title 21 of the Code of Federal Regulations (21 CFR), part 312 (Investigational New Drug Application), Section 32 (IND Safety Reporting) and part 812 (Investigational Device Exemptions), Section 150 (Reports).

16.2 Definitions

Adverse Events (AE)

AE is defined as any untoward medical occurrence in a subject. This definition does not imply that there is a relationship between the adverse event and the device under investigation. An AE can therefore be any unintended sign, symptom, disease or injury or any untoward clinical signs (including an abnormal laboratory findings) in subjects, users or other persons whether or not related to the investigational medical device. The following should be reported as AE:

Doc No: 220CLD

Rev: 03 Date: August 26, 2016

Page 50 of 93

• Untoward medical conditions or signs or symptoms that were absent before starting study treatment.

- Untoward medical conditions or signs or symptoms present before starting study treatment and worsen (increase severity or frequency) after starting study treatment.
- Abnormal laboratory findings.
- Clinical signs or symptoms that require therapy.

Device Deficiency

Device Deficiency is defined as Inadequacy of a medical device related to its identity, quality, durability, reliability, safety or performance, such as malfunction, misuse or use error and inadequate labeling.

Adverse Device Effect (ADE)

ADE is adverse event, related to the use of an investigational medical device. This includes any adverse event resulting from insufficiencies or inadequacies in the instructions for use or the deployment of the device, the operation, or any malfunction of the investigational medical device, device failure or misuse, and any event that is a result of a user error.

Device failures, Malfunctions and Misuse

Investigators are instructed to report all possible device failures, malfunctions or misuse observed during the course of the trial. These incidents will be documented in the case report form provided as follows:

- **Device Failure** A device failure has occurred when the device is used in compliance with the Instructions for Use, but does not perform as described in the Instructions for Use and also negatively impacts treatment of the study subject.
- **Device Malfunction** A device malfunction occurs when an unexpected change to the device that is contradictory to the Instructions for Use is observed, which may or may not affect device performance.
- **Device Misuse** Any use of the investigational device by an investigator that is contradictory to the application described in the Instructions for Use will be categorized as device misuse.

Serious Adverse Events (SAE)

A SAE is an adverse event that:

- 1. Led to a death,
- 2. Led to a serious deterioration in the health of the subject that:
 - a. Resulted in a life-threatening illness or injury
 - b. Resulted in a permanent impairment of a body structure or a body function
 - c. Required in-patient hospitalization or prolongation of existing hospitalization
 - d. Resulted in medical or surgical intervention to prevent permanent impairment to body structure or a body function.

Doc No: 220CLD

Rev: 03 Date: August 26, 2016

Page 51 of 93

3. Led to fetal distress, fetal death or a congenital abnormality or birth defect.

Device deficiencies that might have led to a SAE if a suitable action had not been taken or intervention had not been made or if circumstances had been less opportune are also handled under the SAE reporting system.

However, planned hospitalization for pre-existing condition and/or procedure required by the clinical trial protocol, without serious deterioration in health, is not considered to be a SAE.

Serious Adverse Device Effect (SADE)

A Serious Adverse Device Effect is an adverse device effect that has resulted in any of the consequences characteristic of a serious adverse event.

Unanticipated Serious Adverse Device Effect (USADE)

USADE is defined as serious adverse device effect which by its nature, incidence, severity or outcome has not been identified in the current version of the risk analysis report or other study related documents.

16.3 Anticipated Adverse Events

The Vibrant Capsule targets pathophysiological parameters of chronic constipation by inducing natural bowel activity without using chemical supplements.

Anticipated Adverse Events include those that are reasonably expected to occur in association with a clinical investigation assessing a treatment for functional constipation. Events can occur as a result of the disease or as a result of the treatment (including usage of the home base unit). They may include but are not limited to the following (in alphabetical order):

- Abdominal pain/discomfort/cramping
- Blood in the stool may develop or increase
- Bloating/Flatulence
- Diarrhea
- Nausea may develop or increase
- Rectal pain may develop or increase
- Sensation of vibration in the abdomen
- Uncontrolled leakage of stool may occur
- Vomiting may develop

All events listed above, and additional events that the investigator will evaluate will fit the definition of 'anticipated event', will be categorized as such in the study.

